17. MONITORING

The study monitors will maintain close contact with the Principal Investigator and the Investigator's designated clinical site personnel. The monitor's responsibilities will include:

- Ensuring that the investigation is being conducted according to the protocol, any subsequent amendments, and regulatory requirements are maintained
- Ensuring the rights and wellbeing of subjects are protected

- Ensuring adequate resources, including facilities, laboratories, equipment, and qualified clinical site personnel
- Ensuring that protocol deviations are documented with corrective action plans, as applicable
- Ensuring that the clinical site has sufficient test article and supplies
- Clarifying questions regarding the study
- Resolving study issues or problems that may arise
- Reviewing of study records and source documentation verification in accordance with the monitoring plan

18. ETHICAL AND REGULATORY ASPECTS

18.1. Study-Specific Design Considerations

Potential subjects will be fully informed of the risks and requirements of the study and, during the study, subjects will be given any new information that may affect their decision to continue participation. Subjects will be told that their consent to participate in the study is voluntary and may be withdrawn at any time with no reason given and without penalty or loss of benefits to which they would otherwise be entitled. Only subjects who are fully able to understand the risks, benefits, and potential adverse events of the study, and provide their consent voluntarily will be enrolled.

18.2. Investigator Responsibility

The Principal Investigator is responsible for ensuring that the clinical study is performed in accordance with the signed agreement, the investigational plan, Section 4 of the ICH E6 guidelines on Good Clinical Practice (GCP),² and applicable regulatory requirements. GCP is an international ethical and scientific quality standard for designing, conducting, recording, and reporting studies that involve the participation of human subjects. Compliance with this standard provides public assurance that the rights, safety, and well-being of study subjects are protected, consistent with the principles of the Declaration of Helsinki 64th WMA General Assembly 2013³ and that the clinical study data are credible. The Investigator must maintain clinical study files in accordance with Section 8 of the ICH E6 guidelines on Good Clinical Practice (GCP),² and applicable regulatory requirements.

18.3. Independent Ethics Committee or Institutional Review Board (IEC/IRB)

Before the start of the study, the Investigator (or Sponsor when applicable) will provide the IEC/IRB with current and complete copies of the following documents (where applicable):

- Final protocol and, if applicable, amendments
- Sponsor-approved informed consent form (and any other written materials to be provided to the subjects)
- Investigator's Brochure (or equivalent information) and amendments
- Sponsor-approved subject recruitment materials
- Information on compensation for study-related injuries or payment to subjects for participation in the study

- Investigator's curriculum vitae, clinical licenses, or equivalent information (unless not required, as documented by IEC/IRB)
- Information regarding funding, name of the Sponsor, institutional affiliations, other potential conflicts of interest, and incentives for subjects
- Any other documents that the IEC/IRB requests to fulfill its obligation

This study will be undertaken only after IEC/IRB has given full approval of the final protocol, amendments (if any), the informed consent form, applicable recruiting materials, and subject compensation programs, and the Sponsor has received a copy of this approval. This approval letter must be dated and must clearly identify the documents being approved.

During the study, the Investigator (or Sponsor when applicable) will send the following documents to the IEC/IRB for their review and approval, where appropriate:

- Protocol amendments
- Revision(s) to informed consent form and any other written materials to be provided to subjects
- If applicable, new or revised subject recruitment materials approved by the Sponsor
- Revisions to compensation for study-related injuries or payment to subjects for participation in the study
- Investigator's Brochure amendments or new edition(s)
- Summaries of the status of the study (at least annually or at intervals stipulated in guidelines of the IEC/IRB)
- Reports of adverse events that are serious, unanticipated, and associated with the test articles, according to the IRB's requirements
- New information that may adversely affect the safety of the subjects or the conduct of the study
- Major protocol deviations as required by the IEC/IRB
- Report of deaths of subjects under the Investigator's care
- Notification if a new Investigator is responsible for the study at the clinical site
- Any other requirements of the IEC/IRB

For protocol amendments that increase subject risk, the amendment and applicable informed consent form revisions must be submitted promptly to the IEC/IRB for review and approval before implementation of the change(s).

At least once a year, the IEC/IRB will review and reapprove this clinical study. This request should be documented in writing.

At the end of the study, the Investigator (or Sponsor where required) will notify the IEC/IRB about the study completion. Documentation of this notification must be retained at the clinical site and a copy provided to the CRO or Sponsor as applicable.

18.4. Informed Consent

Each subject must give written consent according to local requirements after the nature of the study has been fully explained. The consent form must be signed before performance of any study-related activity. The consent form that is used must be approved by both the Sponsor and by the reviewing IEC/IRB. The informed consent is in accordance with principles that originated in the Declaration of Helsinki,³ current ICH² and ISO 14155¹ guidelines, applicable regulatory requirements, and Sponsor Policy.

Before entry into the study, the Investigator or an authorized member of the clinical site personnel must explain to potential subject the aims, methods, reasonably anticipated benefits, and potential hazards of the study, and any discomfort it may entail. Subjects will be informed that their participation is voluntary and that they may withdraw consent to participate at any time.

The subject will be given sufficient time to read the informed consent form and the opportunity to ask questions. After this explanation and before entry into the study, consent should be appropriately recorded by means of the subject's dated signature. After having obtained the consent, a copy of the informed consent form must be given to the subject.

18.5. Privacy of Personal Data

The collection, processing and disclosure of personal data and medical information related to the Study Subject, and personal data related to Principal Investigator and any clinical site personnel (e.g., name, clinic address and phone number, curriculum vitae) is subject to compliance with the Health Information Portability and Accountability Act (HIPAA) in the United States⁵ and other applicable personal data protection and security laws and regulations. Appropriate measures will be employed to safeguard these data, to maintain the confidentiality of the person's related health and medical information, to properly inform the concerned persons about the collection and processing of their personal data, to grant them reasonable access to their personal data and to prevent access by unauthorized persons.

All information obtained during the course of the investigation will be regarded as confidential. All personal data gathered in this trial will be treated in strictest confidence by Investigators, monitors, Sponsor's personnel and IEC/IRB. No data will be disclosed to any third party without the express permission of the subject concerned, with the exception of Sponsor personnel (monitor, auditor), IEC/IRB and regulatory organizations in the context of their investigation related activities that, as part of the investigation will have access to the CRFs and subject records.

The collection and processing of personal data from subjects enrolled in this study will be limited to those data that are necessary to investigate the efficacy, safety, quality, and utility of the investigational product(s) used in this study.

These data must be collected and processed with adequate precautions to ensure confidentiality and compliance with applicable data privacy protection laws and regulations. The Sponsor ensures that the personal data will be:

- processed fairly and lawfully
- collected for specified, explicit, and legitimate purposes and not further processed in a way incompatible with these purposes
- adequate, relevant, and not excessive in relation to said purposes
- accurate and, where necessary, kept current

Explicit consent for the processing of personal data will be obtained from the participating subject before collection of data. Such consent should also address the transfer of the data to other entities and to other countries.

The subject has the right to request through the Investigator access to his personal data and the right to request rectification of any data that are not correct or complete. Reasonable steps should be taken to respond to such a request, taking into consideration the nature of the request, the conditions of the study, and the applicable laws and regulations.

Appropriate technical and organizational measures to protect the personal data against unauthorized disclosures or access, accidental or unlawful destruction, or accidental loss or alteration must be put in place. Sponsor personnel whose responsibilities require access to personal data agree to keep the identity of study subjects confidential.

19. STUDY RECORD RETENTION

In compliance with the ICH/GCP guidelines,² the Investigator/Institution will maintain all CRFs and all subject records that support the data collected from each subject, as well as all study documents as specified in ICH/GCP² and all study documents as specified by the applicable regulatory requirement(s). The Investigator/Institution will take measures to prevent accidental or premature destruction of these documents.

Essential documents must be retained until at least two (2) years after the last approval of a marketing application in an ICH region and until there are no pending or contemplated marketing applications in an ICH region or until at least two (2) years have elapsed since the formal discontinuation of clinical development of the investigational product. These documents will be retained for a longer period if required by the applicable regulatory requirements or instructed by the Sponsor. It is the responsibility of the Sponsor to inform the Investigator/Institution as to when these documents no longer need to be retained.

If the responsible Investigator retires, relocates, or for other reasons withdraws from the responsibility of keeping the study records, custody must be transferred to a person who will accept the responsibility. The Sponsor must be notified in writing of the name and address of the new custodian. Under no circumstance shall the Investigator relocate or dispose of any study documents before having obtained written approval from the Sponsor.

If it becomes necessary for the Sponsor or the appropriate regulatory authority to review any documentation relating to this study, the Investigator must permit access to such reports.

If the Investigator has a question regarding retention of study records, he/she should contact JJVC.

20. FINANCIAL CONSIDERATIONS

Remuneration for study services and expenses will be set forth in detail in the Clinical Research Agreement. The Research Agreement will be signed by the Principal Investigator and a JJVC management representative prior to study initiation.

JJVC reserves the right to withhold remuneration for costs associated with protocol violations such as:

- Continuing an ineligible subject in the study
- Scheduling a study visit outside the subject's acceptable visit range

JJVC reserves the right to withhold final remuneration until all study related activities have been completed, such as:

- Query resolution
- Case Report Form signature
- Completion of any follow-up action items

21. PUBLICATION

[figure not shown]
This study will be registered on ClinicalTrials.gov by the Sponsor.

APPENDIX A: PATIENT REPORTED OUTCOMES (STUDY QUESTIONNAIRES)

APPENDIX B: PATIENT INSTRUCTION GUIDE

Patient Instruction Guide (PIG) will be provided separately.

APPENDIX C: PACKAGE INSERT (APPROVED PRODUCT)

ACUVUE® 2 DEFINE™ Vivid Style & LACELLE™ Sparkling Brown

博士伦® 蕾丝炫眸™

软性亲水接触镜 使用说明

致配戴者：很高兴您能选择我公司的软性亲水接触镜（以下简称镜片）。请您在配戴之前仔细阅读，并按眼科医生或专业验配师的指导下使用镜片。）

主要结构、性能）产品名称：软性亲水接触镜（无商品名）Ticon Cosmetic Daily Disposable Soft Contact Lens 产品型号：彩色日抛Cosmetic Daily Disposable 配戴方式：日戴型，最长配戴时间不超过12小时；产品名称：Heflicon A 透氧系数： $11 \times 10^{-11} \text{cm}^2/\text{s} \times [\text{ml}/\text{O}_2/(\text{ml} \times \text{mmHg})]$ 等效于 $8.3 \times 10^{-11} \text{cm}^2/\text{s} \times [\text{ml}/\text{O}_2/(\text{ml} \times \text{hPa})]$ 透氧系数： $11 \times 10^{-11} \text{cm}^2/\text{s} \times [\text{ml}/\text{O}_2/(\text{ml} \times \text{mmHg})]$ 等效于 $8.3 \times 10^{-11} \text{cm}^2/\text{s} \times [\text{ml}/\text{O}_2/(\text{ml} \times \text{hPa})]$ 0mm 基弧半径：8.6mm 含水量：42% 折射率：1.432 后顶焦度范围：0.00D至-12.00D。00D为0.13mm；-0.25D至-12.00D为0.10mm 镜片颜色：蓝色、棕色、紫色、灰色、绿色、绿色、棕色、褐色 内圈：褐色、棕色、紫色、灰色、绿色、水兰色、褐色

注：单色只有虹彩颜色、双色为外圈及虹彩颜色、三色为内、外圈及虹彩颜色。有效期：五年。使用周期：一日。灭菌方法：高温灭菌。贮存：镜片应贮存于干燥、无腐蚀性气体的室内。室内温度控制在-10℃至40℃。保存液类型：氯化钠、硼酸钠、硼酸及纯水调配。

提示：本产品具备抗UV功能，给保护眼睛多一层保障。可以吸收紫外线的软性亲水接触镜并不能替代其它必备的防紫外线眼镜（如护目镜或太阳镜），因为软性亲水接触镜无法完全遮盖眼睛。

（适用范围）镜片用于因屈光不正患者（无禁忌症、18岁以上）近视的视力矫正。

（配戴与摘取）准备工作：配戴前，请眼科医生或专业验配师仔细检查眼睛的健康情况。2、修剪指甲：配戴前修剪指甲，磨光甲缘，以免损伤眼睛和镜片。3、卫生条件：保持配戴环境清洁卫生，并在操作之前用流动的水和中性肥皂彻底洗净双手，用清洁无絮的毛巾擦干或用干手器烘干。4、检查镜片：配戴前先检查镜片是否清洁、柔软、湿润，如镜片破损则不可使用。

如何区分镜片正反面：

1、观察法：将镜片置于手指前端，举至于眼睛水平高度，从侧面观察镜片。如果是正面，镜片侧面将呈碗状半圆形；如果是反面，镜片边缘将向外弯曲，整体呈碟形。2、挤压法：用拇指及食指轻轻挤压镜片一侧边缘，如果是正面，镜片其余边缘部分应向内弯曲；如果是反面，则其余边缘部分向外翻开。

配戴方式：1、洗净双手后取出镜片，将镜片置于食指指尖。2、用双手中指拉开上下眼睑，双眼平视前方或注视下方，将镜片轻轻贴于眼球正中。3、移开食指，转动眼球以确定镜片附着于角膜上，双手中指放松上下眼睑，轻轻眨动双眼，镜片将自然定位。

摘镜方式：1、洗净双手，眼睛平视前方或稍向上看，用双手中指拉开上下眼睑。2、用右手拇指和食指指腹轻轻挤压镜片下边缘，使镜片拱起后将镜片取出。

初次配戴者须知

1、初次配戴隐形眼镜，为使眼睛逐渐适应，请参照右表的时间进行配戴。

2、请在连续配戴1周、1个月、3个月、半年及一年时回原配镜处定期复查，或到眼科医生或专业验配师处进行复查。

（禁忌症、注意事项、警示及提示性说明）1、患有隐形眼镜禁忌症，或工作、生活环境有酸、碱性化学物质及严重污染者请勿使用。2、如有化妆需要，请先戴上镜片再化妆，先摘下镜片再卸妆。3、眼部感觉不适时，可滴数滴专用润滑液，但切勿在配戴同时滴用眼药水，以免缩短镜片使用寿命。4、戴镜时请勿大力揉搓眼睛，以免镜片移位或脱落。5、建议洗脸时不要戴镜，因环境不允许摘镜则请紧闭眼睛，以免镜片被水冲掉或污染镜片。严禁洗澡及游泳时戴镜。6、为保持眼睛健康，建议软性亲水接触镜与框架眼镜交替使用，切勿配戴镜片过夜睡眠。7、如风沙入眼，请摘掉镜片并使用新鲜生理盐水冲洗干净后再配戴，切勿混用沙尘颗粒堵塞镜片。8、为确保镜片质量，请在使用中注意避免以下现象的发生：指甲过长或边缘有毛刺、使用无保护套的尖头镊夹持镜片。9、当发现镜片破损或包装破损时，请更换镜片。10、如在配戴过程中发生眼部不适症状，请立即到眼科医生或专业验配师处进行检查。11、镜片为日戴型镜片，每一天最长使用时间不超过12小时。

开始戴镜天数	1	2	3	4	5	6
戴用时间(小时)	4	6	8	10	12	12

禁忌症

1、眼部疾病：如麦粒肿、睑缘炎等。2、结膜疾病：如重度结膜炎、重度沙眼等。3、角膜疾病：如各种类型的角膜炎、角膜软化症、角膜移植术后。4、泪器疾病：如干眼症、急、慢性泪囊炎等。5、其他疾病：如青光眼、眼部肿瘤等眼部疾病；重症糖尿病、高血压、变态反应性疾病、过氧化物等全身性疾病。6、环境条件：生活环境有严重污染或工作环境有粉尘、酸、碱等挥发性物质，不适合配戴镜片。7、任何角膜感觉失常，敏感度减低。8、眼睛表面或相关组织，对隐形眼镜或保养液过敏。9、眼睛红肿或刺痛感。另外，卫生习惯较差者、精神状况不稳定者、职业环境受限者等须咨询医生意见。在不超出最长配戴时间12小时的前提下，根据医嘱规定确认配戴时间。

（可能风险）

下列因素可能引起眼球损伤。其后果轻则引起一时视力不佳，眼球轻度发炎，严重则眼球永久性损伤或至失明。必须自我防范、警惕。1、镜片配适不良，镜片过松或过紧。2、自我使用不当：例如连续配戴时间过长，导致角膜缺氧，水肿及至擦伤角膜。3、蛋白质沉淀过量且磨坏后，可能刺激角膜球而发炎、损伤。4、镜片护理液使用不当，或选择不当而引起眼睛刺激、发炎、损伤。5、环境因素：洗澡镜片的水污染，细菌在游泳、环境空气污染都可能引起眼球感染。

再次提醒：请按照医生或专业验配师指导下使用本产品。

符号：以下符号可能出现在标套或外包装上。

符号	说明	符号	说明
	无菌		外盒可回收
	详阅使用说明	合格	合格
DIA(Ø _r)	总直径	PWR(Fv)	后顶焦度
LOT	批号	BC(fo)	基弧半径
EXP	失效期	②	禁止二次使用

产品名称：软性亲水接触镜 Ticon Cosmetic Daily Disposable Soft Contact Lens

产品型号：彩色日抛Cosmetic Daily Disposable

生产单位：精华光学股份有限公司

生产单位地址：[name]

生产单位地址：[name]

产地：台湾

执行标准：YZB(台) 3909-2011《软性亲水接触镜》

注册证号：国食药监械(许)字2011第3220100号(更)

服务单位：北京博士伦眼睛护理用品有限公司

注册和经营地址：[name]

电话号码：[name]，服务热线：[name]

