6. STUDY INTERVENTION

6.1. Identity of Test Articles

The following contact lenses will be used in this study:

Table 1: Test Articles

	Test	Control
Name	ACUVUE® 2 DEFINE™ Vivid Style	LACELLE™ Sparkling Brown
Manufacturer	Johnson & Johnson	Bausch and Lomb
Lens Material	Etafilcon A	Hefilcon A
Nominal Base Curve @ 22°C	8.3 mm	8.6 mm
Nominal Diameter @ 22°C	14.0 mm	14.0 mm
Nominal Distance Powers (D)	-2.00 to -7.00 D	-2.00 to -7.00 D
Modality in Current Study	Reusable	Reusable
Replacement Frequency	Two Week	Monthly
Packaging Form (vial, blister, etc.)	Blister	Blister

Each subject will wear approximately 2 of the lenses.

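### The only readable insert in Appendix C is for a one-day disposable lens, but the protocol treats the control as reusable for 11-14 days; the documents do not settle which is wrong

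*Combined protocol and SAP*

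**What the plan says.** The heading of Appendix C names both products: "ACUVUE® 2 DEFINE™ Vivid Style & LACELLE™ Sparkling Brown". The readable text beneath it is a single Chinese-language insert. It gives the product name as "Ticon Cosmetic Daily Disposable Soft Contact Lens" and the model as "产品型号：彩色日抛Cosmetic Daily Disposable", where the Chinese words mean coloured daily disposable. Name and model both appear again at the end of the insert. The insert states a use period of one day, and its symbol legend includes one for no second use.

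The body of the protocol describes a different kind of lens:

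- The protocol title calls both lenses reusable.
- Table 1 in Section 6.1 reads, test then control, "Modality in Current Study Reusable Reusable" and "Replacement Frequency Two Week Monthly".
- Steps 1.31 and 3.20 (Section 7.2) dispense the assigned lens for 11-14 days and supply a care solution.

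Sections 1.4 and 1.5 both refer the reader to Appendix C for the fullest clinical information on the marketed lenses.

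**The concern.** A lens labelled for one day and a lens replaced monthly are different products in use, and the protocol appears to describe the same control as both. Two things are at stake, depending on which text is wrong.

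- **The insert does not apply to the control supplied.** Investigators and ethics committees who follow Sections 1.4 and 1.5 are then sent to another product's wear and risk information. Section 1.4 does list general soft-lens risks and tinted-lens risks, so they are not left with nothing, but that list is not this product's labelling.
- **The insert applies.** The control is then worn well past its stated use period, which is a question of subject safety. The control's follow-up slit-lamp, deposit, wettability, fit, CLUE and logMAR results would describe use outside its labelling. Section 14.7 summarises all observations by lens type, so those summaries would carry this without saying so.

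**Working it through.** This is a comparison of texts. The plan gives no figure to reproduce, and no power or error-rate calculation is involved (Section 14.2 states that the study is not powered for any hypothesis).

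**1. Is the mismatch a reading artefact?** No. The name, model and use-period lines are legible, and the name and model appear twice. Daily wear has not been confused with daily disposable either: the insert states the daily-wear mode separately from the daily-disposable model and the one-day use period.

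**2. The two descriptions side by side**

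| Attribute | Appendix C insert | Protocol body (control) |
|---|---|---|
| Type | Daily disposable | Reusable (title, Table 1) |
| Replacement | One-day use period | Monthly (Table 1) |
| Wear in the study | Not applicable | 11-14 days with care solution (steps 1.31, 3.20) |
| Material | Printed as Heflicon A | Hefilcon A (Table 1) |
| Base curve | 8.6 mm | 8.6 mm (Table 1) |
| Manufacturer | "生产单位：精华光学股份有限公司" | "Bausch and Lomb" (Table 1) |

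**3. Does the insert belong to the control?**

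Evidence for:
- The insert opens with a brand line carrying the Chinese name of Bausch & Lomb and a trademarked product name.
- Its service unit is a Bausch & Lomb company.
- Base curve and material agree with Table 1, apart from the spelling.

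Evidence against:
- The product-name line, "产品名称：软性亲水接触镜（无商品名", states that there is no trade name.
- The manufacturer line differs from Table 1.
- The change history records that version 2.0 changed the control variant, without naming the old or the new one. An insert could have been left over from that change, but the documents do not say so.

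The documents do not show whether the Chinese product name in the brand line is the control's name, so that line does not decide the matter.

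**4. Size under each reading**

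- Insert does not apply: no wear exceeds labelling. The fault lies in Appendix C and the two sections that rely on it.
- Insert applies, and the same pair is worn through the period: a use period of 1 day against 11-14 days of wear, that is 11/1 = 11 to 14/1 = 14 times the stated period.

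**5. Which data are touched?** Section 2.2 sets the primary endpoint at lens fit (steps 1.21 and 3.10), on the day the lens is first inserted. It falls inside even a one-day use period. The exposed data are those from the follow-up to the control period, at Visit 2 or Visit 4 according to sequence, including the exit slit-lamp examination.

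**The case against.** The strongest reply is that the operative text on reuse is consistent. Title, Table 1 and dispensing steps agree, the study is descriptive with no hypotheses, and the primary endpoint is untouched, so the fault may be no more than a wrong attachment. That limits the consequence for the analysis. It does not remove the conflict, because Sections 1.4 and 1.5 give the appendix a working role and the alternative reading concerns subject safety.

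A second reply is that Table 1's modality row refers to the current study and could signal deliberate reuse of a one-day lens. The row below it does not fit that. Monthly cannot be the study schedule when wear lasts 11-14 days and the synopsis gives two weeks, so it reads as a product attribute, and it contradicts the insert.

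A third is that lenses could be changed daily under the general supply and accountability text in Sections 6.3 and 6.7. Neither section sets a daily change, and supplying care solution fits reuse.

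Some stronger readings are tempting but unsupported:

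- A reader might infer that subjects are being given a one-day lens to reuse. The manufacturer and trade-name lines leave open that the insert belongs to another product.
- A reader might equally infer that the insert is simply mis-attached. The brand line, service unit, base curve and material count against assuming so. Nothing in the documents supports ranking the two.
- A reader might take the Section 6.1 remark that each subject wears about two lenses, or the Section 4.1 remark on replacement at Visit 3, as proof that no daily supply exists. In a bilateral crossover, 2 eyes × 2 treatments already needs 4 lenses, so the first probably counts lens types. The second may only describe the switch of treatment.
- A reader might conclude that the correct control insert, or the test-lens insert, was never attached. Either may be present but unreadable in the text available here.

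**Conclusion.** The mismatch is certain; which side is wrong is not, and no likelihood is assigned to either. Its size depends on the labelling of the lens actually supplied. Either no wear is beyond labelling and the appendix misdirects its readers, or a lens with a one-day use period is worn for 11-14 days. The second case assumes that one pair is worn through the period, which the care solution suggests but no step states outright.

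The primary endpoint, sample size and error rates are not affected. Nothing is claimed about what subjects are told, because Appendix B says that the Patient Instruction Guide is provided separately. The point should be fixed; it is more than clerical because it bears on safety information and on what the control's follow-up summaries represent. It would become more serious if the check shows that the insert applies.

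**What to change.** The sponsor should:

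1. Check the labelling of the control product and variant actually supplied.
2. Confirm that the insert for that variant is the one in Appendix C.
3. Reconcile Appendix C, Table 1, the synopsis and steps 1.31 and 3.20 with that labelling, and re-check Sections 1.4 and 1.5 against it.
4. Record in the amendment which text was corrected and, if follow-up data already exist, state in the study report which labelling applied to the control.

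No wear, reuse or replacement rule is proposed here; that is for the sponsor to settle from the labelling. The cost is one labelling check and a short protocol amendment, with no added subjects or procedures.
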